## **8.2. Primary Efficacy Analysis**

There is no primary efficacy endpoint in this study, therefore no primary efficacy analysis is performed.

## **8.3. Secondary Efficacy Analysis**

Secondary efficacy endpoints are listed in Section [3.2.2](#).

[figure not shown]
The secondary efficacy outcome of achievement or maintenance of clinical response will be based on the proportion of patients who achieve or maintain clinical response at end of treatment compared to APD334-003 baseline using the MITT and CP populations. Summary statistics i.e. total number of patients (N), frequencies (n), proportion (%) and its 90% CI for patients that achieved or maintained clinical response (responders) at end of treatment in APD334-005 will be produced as described in Section [4](#).

[figure not shown]
Similar summary statistical analyses will be produced for the second secondary efficacy outcome i.e. clinical remission at Week 46 compared to APD334-003 baseline.

Each secondary efficacy endpoint will be summarized, within the same presentation, by the following:

- Proportion of patients that achieved clinical response/clinical remission at Week 12 in APD334-003
- Proportion of patients that achieved clinical response/clinical remission at end of treatment in APD334-005
- Proportion of patients that achieved clinical response/clinical remission at both Week 12 in APD334-003 and end of treatment in APD334-005

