## 6.12 Concomitant Medications and Procedures

All medications (OTC and prescribed) that are taken by patients and all procedures that are performed during the screening period and during the study must be recorded in the electronic case report form (eCRF) with start date/time and stop date/time, if known. Concomitant medication for medical conditions other than UC are permitted as clinically indicated patient to specific protocol requirements outlined in Sections 4.2 and 4.3 of study protocol APD334-003.

The following should be taken into account with regard to concomitant procedures:

- Patients may not undergo major elective surgery while enrolled in this study.
- Patients may not donate sperm, or oocytes during the study and for 30 days after the last dose of study drug.

[REDACTED]

[REDACTED]

[REDACTED]

[REDACTED]

[REDACTED]

[REDACTED]

[REDACTED]

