### 6.12.2 Excluded Medications

The following medications are excluded from the study:

- Treatments for UC other than those listed in Section 6.12.1 (either approved or investigational)
- All live vaccines, during study treatment and for at least 6 months after the last dose of study drug

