## 6.13 Removal of Patients from the Trial or Study Drug

The study may be terminated early if, in the opinion of the sponsor, investigator, or IRB/IEC, an unacceptable risk to the safety and welfare of patients is posed by the continuation of the study in light of review of the key safety data.

Patients will be free to withdraw from the study at any time should they so wish. A patient may be withdrawn from the study for any of the following reasons (including but not limited to):

- Clinical investigator may remove a patient if, in his/her opinion, it is in the best interest of the patient [REDACTED]
- Withdrawal of consent - Any patient may withdraw his/her consent from the study at any time. The investigator should make a reasonable attempt to document the specific reason why consent was withdrawn.
- Deviation/noncompliance with the protocol or study drug
- An adverse event
- Lost to follow up

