### 9.6.1 Data Analysis for Secondary Efficacy Endpoints

The secondary efficacy outcome of achievement or maintenance of clinical response will be based on the proportion of patients who achieve or maintain clinical response [defined as a decrease in 3-component Mayo Clinic score of  $\geq 2$  points and at least 30% with either a decrease of rectal bleeding of  $\geq 1$  or rectal bleeding score of 0 or 1] at Week 46 compared to APD334-003 baseline using the ITT population. All patients who prematurely discontinue for any reason will be considered failures (non-responders) for all the proportion based endpoints. Similar analyses will be performed in terms of the other Week 46 proportion based endpoints such as proportion of patients achieving clinical remission and proportion of patients with endoscopic improvement.

For each study visit during the study, stool frequency and rectal bleeding subscores will be derived

- [Redacted bullet point]
- [Redacted bullet point]
- [Redacted bullet point]

All patients who prematurely discontinue for any reason will be considered failures (non-responders) for all the proportion based endpoints.

Descriptive statistics of N, mean or mean change, and standard deviation will be produced for continuous efficacy endpoints.

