### **3.2.2. Secondary Endpoints**

Secondary efficacy endpoints are achievement, durability and maintenance of clinical response and/or clinical improvement. They include the following:

- The proportion of patients who achieve clinical response at end of treatment in APD334-005; the proportion of patients who achieve clinical response at Week 12 in APD334-003 and maintain clinical response at end of treatment in APD334-005. [definition of clinical response: a patient has achieved clinical response if he/she meets criteria of clinical remission defined below, or meets criteria of clinical response i.e. a decrease in 3-component Mayo Clinic score of  $\geq 2$  points and at least 30% with either a decrease of rectal bleeding of  $\geq 1$  or rectal bleeding score of 0 or 1] at Week 46 compared to APD334-003 baseline]
- The proportion of patients who achieve clinical remission at end of treatment in APD334-005; the proportion of patients who achieve clinical remission at Week 12 in APD334-003 and also maintain clinical remission at end of treatment in APD334-005 [definition of clinical remission: individual subscores of the 3-component Mayo Clinic score as follows: an endoscopy score (using flexible proctosigmoidoscopy) of 0 or 1 (excluding friability), a rectal bleeding score of 0 or 1, and a stool frequency score of 0 or 1 with a decrease of  $\geq 1$  point] at Week 46 compared to APD334-003 baseline]

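### On the visible text, response and remission are scored without regard to excluded ulcerative colitis treatment, so a patient who takes it and stays in the study can count as a responder or maintainer

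*SAP*

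**What the plan says.** **Endpoint definitions.** SAP 3.2.2 says that "a patient has achieved clinical response if he/she meets criteria of clinical remission defined below, or meets criteria of clinical response". The response criteria are a fall in the 3-component Mayo score plus a rectal bleeding condition. For remission it gives a "definition of clinical remission: individual subscores of the 3-component Mayo Clinic score as follows", followed by thresholds for endoscopy, rectal bleeding and stool frequency. Neither definition has a condition on other UC treatment. The protocol's versions (Study Definitions, 9.5.1, 9.6.1) have none either.

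**Summaries.** SAP 8.3 tabulates the "Proportion of patients that achieved clinical response/clinical remission at end of treatment in APD334-005" and, for maintenance, the "Proportion of patients that achieved clinical response/clinical remission at both Week 12 in APD334-003 and end of treatment in APD334-005".

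**Excluded treatment.** Protocol 6.12.2 excludes "Treatments for UC other than those listed in Section 6.12.1 (either approved or investigational"). The permitted list in 6.12.1 is not visible.

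**Withdrawal.** Protocol 6.13 says: "A patient may be withdrawn from the study for any of the following reasons (including but not limited to"). Deviation from, or noncompliance with, the protocol or study drug is one of the reasons listed.

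**Failure rule.** Protocol 9.6.1 says: "All patients who prematurely discontinue for any reason will be considered failures (non-responders) for all the proportion based endpoints". No other event is visibly treated as failure.

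**Data available.** Protocol 6.12 requires recording of "All medications (OTC and prescribed) that are taken by patients", with start and stop dates where known. SAP 7.1 codes, summarises and lists medications taken during treatment. SAP 5.2 summarises and lists protocol deviations. Neither section links these data to efficacy.

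**The concern.** The secondary objective (Protocol 2.2, SAP 2.2) is the effect of APD334 on achieving and maintaining response or remission. The protocol excludes other UC treatments, yet the visible scoring takes no account of whether one was used. Good scores reached after such treatment are credited to APD334.

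Maintenance is the most exposed summary. A Week 12 responder who relapses, is treated with another drug and is quiet again at end of treatment looks the same in that row as a patient whose response never lapsed.

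The situation is foreseeable. Treatment lasts 34 weeks, Amendment 04 admits all APD334-003 completers and not only responders, and Protocol 6.9.4 anticipates unscheduled visits for disease exacerbation. The plan makes no formal between-group comparison, so each proportion is read largely at face value.

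**Working it through.** The plan gives no sample size, expected rate or frequency of excluded treatment, so there is no figure to reproduce. The check is a trace through the visible rules, then an illustration of scale.

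**1. Trace of one patient.** A Week 12 responder enters APD334-005, takes an excluded UC treatment during the 34 weeks, stays in, and meets the scores at end of treatment.

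- Withdrawal (Protocol 6.13): deviation is a reason for which a patient may be withdrawn. No visible text makes withdrawal follow. By contrast, Protocol 6.11.2.1 states outright that pregnant patients will be discontinued.
- Failure rule (Protocol 9.6.1): not triggered, because the patient did not discontinue.
- MITT (SAP 4.4.1): needs a dose, a baseline and a post-enrolment measurement. The patient is included.
- Completers population (SAP 4.4.2): MITT plus completion status. A patient who completes is included.
- Endoscopy carried forward (SAP 4): no condition on treatment taken before the endoscopy.
- Definitions (SAP 3.2.2): met on scores.
- Listed changes (visible SAP 12): both definitions are altered, and no rule on excluded treatment is added.

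Result: the patient counts in the end-of-treatment row and in the maintenance row, in both populations. Comparing MITT with completers would not expose this, because both keep the patient.

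**2. Scale (all inputs assumed).** Let u be the share of analysed patients who take an excluded UC treatment and stay in, r the fraction of those who meet response at end of treatment, and c the fraction of those responders who would have responded anyway.

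Overstatement = u × r × (1 − c)

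| u | r | c = 0 (upper bound) | c = 0.5 | c = 1 |
|---|---|---|---|---|
| 0.03 | 0.5 | 0.03 × 0.5 = 1.5 points | 0.75 points | 0 |
| 0.10 | 0.5 | 0.10 × 0.5 = 5 points | 2.5 points | 0 |

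**3. Effect of reclassification on the reported row.** Here the input is the share s of responders who used excluded treatment. With response rate p, the reported rate falls by p × s. For p from 40% to 60% and s from 5% to 20%, that is 0.40 × 0.05 = 2 points up to 0.60 × 0.20 = 12 points. With an assumed N of 100 and 60 responders (exact 90% CI, the level that the SAP uses):

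- as observed: 60.0% (51.3 to 68.2)
- 3 reclassified (s = 5%): 57.0% (48.3 to 65.4)
- 6 reclassified (s = 10%): 54.0% (45.3 to 62.5)
- 12 reclassified (s = 20%): 48.0% (39.4 to 56.7)

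Steps 2 and 3 use different assumed inputs, so neither confirms the other. Together they show that the size depends entirely on a frequency that the documents do not give.

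**The case against.** **Missing text.** A rule could sit in text that cannot be read. Protocol 5.6 is redacted and 6.12.1 is not visible. Parts of Protocol 6.13 and 9.6.1 are redacted, and parts of SAP 4, 8.3 and 8.4 are redacted or not shown. This stands. A reader might infer that the plan has no handling rule at all, and the documents do not support that. They support only that the readable definitions, failure rule and populations contain none.

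**The word "may".** In Protocol 6.13 it introduces a mixed list that also includes withdrawn consent and loss to follow-up, so it is not evidence that users of excluded treatment are kept in. If they leave, the protocol's discontinuation rule makes them failures. This is fair on frequency, but the scoring gap remains for any who stay. That the visible SAP does not restate the discontinuation rule is a separate matter.

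**Direction.** A reader might infer that ignoring excluded treatment always inflates the estimate. It does not: a patient who would have responded anyway adds no bias, and the proposed rule would score that patient as a failure. The 1.5–5 points are therefore an upper bound under their assumptions.

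**Descriptive study.** The primary objective is safety, there are no hypotheses, and medications and deviations are listed, so as-observed counting can be defended and use can be seen. That limits the seriousness. But a reader of the response table would have to match listings patient by patient to learn how many responders were affected.

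**Limits of the remedy.** It does not reach added or increased use of permitted UC drugs, and it has no duration threshold. Both points stand. A pre-specified list and the as-observed row make the choice transparent, but the adjusted rate should not be presented as free of all confounding.

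**Conclusion.** The point holds on the visible text. A patient who takes an excluded UC treatment, is not withdrawn and meets the scores at end of treatment counts as a responder or remitter, and as a maintainer if the same criteria were met at Week 12. This can overstate the effect attributed to APD334.

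The size is unknown. If 3–10% of patients did this and half met response, the overstatement is at most 1.5–5 percentage points, falling to zero if all of them would have responded anyway. Those inputs are assumptions, not trial data.

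The consequence is for interpretation of the secondary proportions. The primary safety objective is untouched, and with no hypothesis tests there is no type I error to protect. The change is still worth making: the needed data are already collected, and it extends the composite approach that the protocol already takes to discontinuation.

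**What to change.** If the redacted or missing text already contains a rule, add a cross-reference in SAP 8.3. If not, add the following there:

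- Classify as non-responder and non-remitter any patient who took a UC treatment excluded by Protocol 6.12.2 between the first APD334-005 dose and the end-of-treatment assessment.
- Identify these patients by medical review of the coded concomitant medications before database lock, against a pre-specified list.
- Apply the rule identically to every treatment column in SAP 4, including the placebo column from Amendment 02, so that differing use does not distort a descriptive reading across columns.
- Report the number reclassified in each column, and show the as-observed proportion with its 90% CI alongside as a sensitivity row.
- List the change in SAP 12. If the database is already locked, document it with its reason in the clinical study report, as Protocol 9 and SAP 1 provide.

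The cost is a small medical review, one flag, and possibly slightly lower reported rates. Some patients who would have responded anyway will count as failures; the as-observed row shows how far that could matter. This is an analysis classification only and does not change which treatments are permitted.

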#### **8.4. Exploratory Efficacy Analyses**

## 8.6. Multiplicity

Multiplicity is not applicable for this study.

## 9. SAFETY ANALYSIS

The safety of etrasimod will be monitored throughout the study with safety endpoints being as follows:

- Treatment-emergent adverse events (TEAEs) up to 30 days following discontinuation of the study drug
- Treatment-emergent serious adverse events (SAEs) up to 30 days following discontinuation of the study drug

Additional safety assessments will include:

- Physical & neurological examinations including ophthalmoscopy (and optical coherence tomography [OCT], where available)
- Progressive multifocal leukoencephalopathy (PML) checklist
- Clinical laboratory tests to include hematology, serum chemistry, coagulation, and urinalysis
- Vital sign measurements
- Pulmonary Function Tests (PFTs)
- ECGs
- AE reporting

For analyses based on laboratory measurements, vital signs and ECGs, summary tabulations (n, mean, SD, median, minimum and maximum for actual and change [or percent change] from baseline) will be presented. For analyses based on AEs, frequency and percentage will be presented. The analyses for all safety outcomes (categorical or continuous measures) will use the Safety population.

For analysis based on laboratory measurements, at least 1 laboratory test post-enrollment measurement in the extension study is required for inclusion in the Safety population. When assessing change from baseline, a baseline measurement is also required. Baseline for the safety analysis is defined as the last pre-enrollment measurement (i.e. APD334-005 Day 1 pre-dose). No missing data will be imputed for the safety analysis.

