### 6.6.3 ECG Assessment

Safety ECGs will be performed as outlined in Appendix 1, schedules of procedures and events. Post-screening ECGs will be compared with screening ECG.

The PI or sub-investigator (physician) will be responsible for review and interpretation of safety ECG on site and determining if the ECG is normal, abnormal “not clinically significant” or abnormal “clinically significant”. Findings will be documented in the CRF. This information will be used in the continuous safety review during the conduct of the trial. The ECGs will also be read and interpreted by the central ECG laboratory.

[REDACTED]

[REDACTED]

[REDACTED]

[REDACTED]

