#### 6.11.3 Assessment of Adverse Event Severity

The severity of each AE will be assessed at onset by a nurse and/or physician. When recording the outcome of the AE the maximum severity of the AE experienced will also be recorded. The severity of the AE will be graded according to the CTCAE v4.03 definitions, listed below:

- **Grade 1:** Mild; asymptomatic or mild symptoms; clinical or diagnostic observations only; intervention not indicated.

- **Grade 2:** Moderate; minimal, local or noninvasive intervention indicated; limiting age-appropriate instrumental Activities of Daily Living (ADL)\*.
- **Grade 3:** Severe or medically significant but not immediately life-threatening; hospitalization or prolongation of hospitalization indicated; disabling; limiting self-care ADL\*\*.
- **Grade 4:** Life-threatening consequences; urgent intervention indicated.
- **Grade 5:** Death related to AE.

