## **2. OBJECTIVES**

### **2.1. Primary Objective**

[figure not shown]
The primary objective of this study is to evaluate the long-term safety and tolerability of etrasimod in patients with ulcerative colitis who have completed the APD334-003 study.

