#### 3.2. Study Endpoints

##### 3.2.1. Primary Endpoint

The primary endpoint for the study is long-term safety. The safety of etrasimod will be monitored throughout the study with safety endpoints being as follows:

- Treatment-emergent adverse events (TEAEs) up to 30 days following discontinuation of the study drug

[figure not shown]
- Treatment-emergent serious adverse events (SAEs) up to 30 days following discontinuation of the study drug

[figure not shown]

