## **9.2. Clinical Laboratory Evaluations**

Clinical laboratory evaluations (i.e. hematology, serum chemistry, coagulation and urinalysis) will be performed by a central laboratory. All summaries will be based on the units provided by the central laboratory, no conversion will be performed.

Summary tabulations (i.e. n, mean, SD, median, minimum and maximum) for the observed values and changes from baseline will be presented for clinical laboratory evaluations with numeric values for patients in the Safety population. Observed results at each visit and changes from baselines (APD334-003 baseline and APD334-005 baseline) to each scheduled post-baseline visit will be presented.

All relevant clinical laboratory tests will be classified as Low, Normal, and High according to the normal ranges. This categorical data will be summarized in shift tables comparing the results at last scheduled post-baseline visit with those at the baseline visit. Baseline for APD334-003 study is defined as last measurement before first dose of study medication in APD334-003 study, and baseline for APD334-005 study is defined as last pre-enrollment measurement (APD334-005 Day 1 pre-dose).

If any laboratory value falls above or below the upper or lower level of quantification, the value of the upper or lower level of quantification will be taken (e.g.  $<0.2$  will become 0.2) for summaries but left as recorded in the listing.

All individual lab values will be listed by visit.

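### Laboratory shift tables use only Low/Normal/High at the last scheduled visit, so marked or transient abnormalities are counted by patient only if recorded as adverse events

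*SAP*

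**What the plan says.** SAP 2.1 sets the purpose: "The primary objective of this study is to evaluate the long-term safety and tolerability of etrasimod in patients with ulcerative colitis". SAP 3.2.1 adds: "The primary endpoint for the study is long-term safety", and names treatment-emergent adverse events and serious adverse events as the endpoints. SAP 9 lists laboratory tests, vital signs and ECGs as additional safety assessments.

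The planned summaries are these:

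- **Laboratory values, vital signs and ECGs (SAP 9):** "summary tabulations (n, mean, SD, median, minimum and maximum for actual and change [or percent change] from baseline) will be presented".
- **Laboratory categories (SAP 9.2):** "All relevant clinical laboratory tests will be classified as Low, Normal, and High according to the normal ranges". The section continues: "This categorical data will be summarized in shift tables comparing the results at last scheduled post-baseline visit with those at the baseline visit". Individual values are listed by visit. No text in this section is blacked out.
- **Adverse events (SAP 9.1 and 9.1.4):** events are counted by preferred term and by grade, with a separate table for Grade 3 and above. On grading, Protocol 6.11.3 says: "The severity of the AE will be graded according to the CTCAE".
- **ECG reading (Protocol 6.6.3):** the site classes each tracing as normal, abnormal without clinical significance, or abnormal with clinical significance. "Findings will be documented in the CRF".

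Under Protocol 5.5.2 and SAP 4.3.2 the sponsor, patients and study personnel stay blinded to total white cell and lymphocyte counts. A central CRO physician monitors them.

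**The concern.** Laboratory safety signals are mostly excursions in a few individuals. The useful question is how many patients reached a given degree of abnormality at any time on drug. The SAP 9.2 shift table cannot answer it, for two reasons.

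First, three categories merge degrees. A liver enzyme just above the normal range and one several times the upper limit of normal (ULN) both count as High. For lymphocytes, SAP 1 describes a reduction in the peripheral count as part of the drug's mechanism, so Low says little about severity.

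Second, the comparison uses one late visit. A value that was markedly abnormal mid-study and then recovered appears as whatever it was at the end.

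At stake is whether the study report can state, from systematic data, how many patients had a marked laboratory abnormality during up to 34 weeks of treatment.

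**Working it through.** The documents give no sample size, threshold or expected count on this point, so there is no planned figure to reproduce. The check is a reading of the text, with arithmetic on assumed inputs to show scale. Assumed: N = 50, 100 or 150 patients; 4, 6 or 8 post-baseline laboratory visits; the abnormality sizes below. The readable text gives neither N nor the visit schedule.

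**1. What a last-visit table catches.** Suppose an abnormality lasts one visit and is equally likely at any of V visits. The share seen at the last visit is 1/V:

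- V = 4: 1/4 = 25%
- V = 6: 1/6 = 17%
- V = 8: 1/8 = 13% (12.5%)

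An abnormality that persists to the end is always caught, so the loss falls on those that resolve. The readable text also does not say whether the last scheduled visit is end of treatment or the 2-week follow-up, when patients are off drug (Protocol 7.2.2.5).

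**2. What the descriptive statistics show.** Suppose k patients rise from 0.6 to 5 times ULN at the same visit and the rest do not change. The mean shifts by k × (5 − 0.6)/N = 4.4k/N, in multiples of ULN:

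| N | k = 1 | k = 3 |
|---|---|---|
| 50 | 0.088 | 0.264 |
| 100 | 0.044 | 0.132 |
| 150 | 0.029 | 0.088 |

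The maximum would be 5 times ULN whether k is 1 or 3. It reveals that such a case exists, but not the number of patients.

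**3. What a count would add.** At an assumed true rate of 2%, the chance of at least one case is 1 − 0.98^N: 64%, 87% and 95% at N = 50, 100 and 150. If two cases were seen, the exact (Clopper-Pearson) 90% interval, the level the SAP uses elsewhere, would be 0.7–12.1%, 0.4–6.2% or 0.2–4.1%. A count with its denominator is therefore informative at these sizes.

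**4. Whether the adverse event tables supply the count.**

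- Protocol 6.8 leaves it to the physician to judge whether an abnormal value is an adverse event. Protocol 9.8.5 says a clinically significant change may be recorded as one if the investigator or sponsor thinks fit. What enters the Grade 3 and above table therefore depends on judgement.
- For lymphocytes, the sponsor and site personnel who would make that judgement do not see the result (Protocol 5.5.2, SAP 4.3.2). The central physician does, but no readable text turns that review into a table.

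**5. ECG, vital signs and the separate lymphocyte section.** No threshold count is visible in SAP 9.3, 9.5 or 9.6, and no visible table uses the site ECG interpretation. However, SAP 9.3 ends at a figure that is not shown. The SAP 9.5 heading is partly redacted in the contents, and its readable text lists intervals without an analysis paragraph. SAP 9.6 has redacted gaps, and Protocol 9.8.6 ends in redaction. Absence cannot be established there.

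**The case against.** The strongest defence is that the named primary safety endpoints are adverse events and serious adverse events, which are counted by term and grade. Laboratory values are an additional assessment in a descriptive study without hypothesis tests, and no stated commitment is broken. The tables give median, SD, minimum and maximum as well as the mean. They are split by previous APD334-003 treatment, so extremes show up in smaller columns, and individual laboratory values are listed. A central physician watches the lymphocyte counts, and SAP 12 promises report text on five patients with blood-count follow-up at local laboratories.

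Most of this stands, and it limits the point. A reader might infer that severe abnormalities are never counted, that ECGs and vital signs are summarised only by means, or that large individual changes would go unnoticed. The documents do not support any of these. Events recorded as adverse events are counted, including a table for Grade 3 and above. The summaries go beyond means. A large individual change would appear as a minimum or maximum change. For ECG, heart rate and SAP 9.6, redaction prevents any claim that threshold counts are missing. Nor do the documents give a figure for how many treated patients would be classed as Low for lymphocytes.

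The defence does not reach the SAP 9.2 rule itself. A listing leaves the counting to the reader, an extreme is not a count, and a discretionary adverse event route does not replace a systematic tabulation.

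**Conclusion.** The concern holds for laboratory data. Followed as written, the shift table in SAP 9.2 merges slight with marked abnormalities and drops those that resolve before the last scheduled visit. Nothing in that unredacted section provides a patient count by degree. The adverse event tables fill the gap only in part, and hardly at all for lymphocytes.

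The size cannot be fixed from the documents. On the assumptions shown, the last-visit rule would catch 13% to 25% of one-visit abnormalities, and those it caught would carry no degree. The conclusion about the rule does not depend on those numbers, only on the wording of SAP 9.2.

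For vital signs and ECG the supportable statement is narrower: no threshold count is visible, and the sponsor should confirm what is planned. This is a change that should be made for a study with a primary safety objective. It is not an error that invalidates the planned adverse event analysis.

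**What to change.** In SAP 9.2, add to the current shift table, or replace it with, a shift from each baseline (APD334-003 and APD334-005) to the worst on-treatment value, with n (%) of patients. Use CTCAE v4.03 grades or other categories chosen by the sponsor and fixed before database lock. Cover key analytes, including lymphocytes, neutrophils, platelets, ALT, AST, bilirubin and creatinine, with direction of worst stated for each. Define the on-treatment window, so that off-drug follow-up values are handled by rule. The protocol applies CTCAE to adverse event severity; applying it to laboratory values is an extension that the SAP would have to state.

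For SAP 9.3 and 9.5, the sponsor should confirm whether two items are already planned: n (%) of patients beyond pre-specified vital-sign and ECG limits, and a shift of the recorded ECG interpretation from baseline to worst. Add them if not.

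The cost is a few extra tables from data already collected, plus agreement on cut-offs before lock. If lock has passed, SAP 1 already provides for major changes to be documented with their rationale in the study report.
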